#### 7.1.4 **Other Procedures**

#### 7.1.4.1 Withdrawal/Discontinuation

When a subject discontinues/withdraws prior to active trial completion, the subject will need to sign a withdrawal consent. If the subject becomes cognitively impaired while on this study the subject and/or their Legal Representative will have the opportunity to sign a withdrawal consent. All applicable activities scheduled for the final trial visit should be performed at the time of discontinuation/withdrawal. Any adverse events which are present at the time of discontinuation/withdrawal should be followed in accordance with the safety requirements outlined in Section 7.2 - Assessing and Recording Adverse Events. After discontinuing treatment following completion, subjects should return to the site for a Safety Follow-up Visit (described in Section 7.1.5.) and then proceed to the Follow-Up Period of the study (described in Section 7.1.5.4).

Subjects will have the option to withdraw from the study completely or partially which will allow following for progression/survival.

#### 7.1.4.2 **Blinding/Unblinding**

There is no blinding for this trial.

#### 7.1.5 Visit Requirements

Visit requirements are outlined in Section 6.0 - Trial Flow Chart. Specific procedure-related details are provided above in Section 7.1 - Trial Procedures.

#### 7.1.5.1 Screening

#### 7.1.5.1.1 Screening Period

Approximately 28 days prior to treatment (day-36), potential subjects will be evaluated to determine that they fulfill the entry requirements as set forth in Section 5.1. Visit requirements are outlined in Section 6.0 - Trial Flow Chart.

Results of a test performed prior to the subject signing consent as part of routine clinical management are acceptable in lieu of a screening test if performed within the specified time

frame. Screening procedures are to be completed within 28 days prior to the first dose of trial treatment except for the following:

• Laboratory tests and ECOG performance status are to be performed within 14 days prior to the first dose of trial treatment.

• For women of reproductive potential, a urine pregnancy test will be performed within 72 hours prior to the first dose of trial treatment.

• Biopsy collections may be collected up to 60 days prior to enrollment as presented in Sections 5.1.1 and 6.1.

#### 7.1.5.2 **Treatment Period**

Visit requirements are outlined in Section 6.0 - Trial Flow Chart. Specific procedure-related details are provided above in Section 7.1 - Trial Procedures.

#### 7.1.5.3 **Post-Treatment Visits**

Subjects will be followed for up to 5-years following treatment completion. The Trial Flow Chart – Section 6 outlines visit requirements and study procedures required at these visits. Further details are outlined in the subsections below.

#### 7.1.5.4 Safety Follow-Up Visit

The mandatory Safety Follow-Up Visit should be conducted approximately 30 days after the last dose of trial treatment or before the initiation of a new anti-cancer treatment, whichever comes first, for those subjects who do not complete active treatment. All AEs that occur prior to the Safety Follow-Up Visit should be recorded. Subjects with an AE of Grade > 1 will be followed until the resolution of the AE to Grade 0-1, return to baseline, or until the beginning of a new anti-neoplastic therapy, whichever occurs first. SAEs that occur within 90 days of the end of treatment or before initiation of a new anti-cancer treatment should also be followed and recorded.

#### 7.1.5.5 Follow-up Visits

Follow-up visits for subjects who complete study treatment are outlined in the Trial Flow Chart – section 6.

Subjects who discontinue trial treatment for a reason other than disease progression will move into the Follow-Up Phase. Every effort should be made to collect information regarding disease status until the start of new anti-cancer therapy, disease progression, death, or end of study. Information regarding post-study anti-cancer treatment will be collected if new treatment is initiated.

#### 7.1.5.6 Survival Follow-up

Once a subject experiences confirmed disease progression or starts a new anti-cancer therapy, the subject moves into the Survival Follow-Up Phase. These subjects will be followed every 6 months to assess for survival status until death, withdrawal of consent, or the end of the study, whichever occurs first.

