#### 3.2 Secondary Objective(s) & Hypothesis (es)

1. **Objective:** To estimate progression-free survival (PFS), overall survival (OS), the locoregional control rate (LRC), and distant metastases (DM) rate at 1- and 2-years in subjects treated with pembrolizumab given in combination with CRT.

**Hypothesis**: The addition of pembrolizumab to standard CRT will show increased efficacy in terms of key survival endpoints utilized in head and neck cancer.

2. **Objective:** To determine the best overall response rate (ORR) as defined by RECIST 1.1 at treatment end imaging in subjects with Stage III-IVB SCCHN treated with pembrolizumab given in combination with CRT.

**Hypothesis**: The addition of pembrolizumab to standard CRT will show superior ORR compared to historical controls.

4. **Objective:** To estimate the quality of life (QOL) of subjects with Stage III-IVB SCCHN treated with pembrolizumab in combination with CRT during therapy, treatment end, and 1- and 2-years following treatment.

**Hypothesis**: Acute and long-term QOL of participants treated with the combination of pembrolizumab and low dose weekly cisplatin and radiation will be superior to historical controls.

5. **Objective:** To correlate ORR, PFS, OS, LRC, and DM with tumor PD-L1 expression in subjects with Stage III-IVB SCCHN treated with pembrolizumab in combination with CRT.

**Hypothesis**: High PD-L1 expression has correlated with responses in the metastatic setting and will correlate with key disease response and survival outcomes in the curative intent setting.

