#### 5.9 Subject Withdrawal/Discontinuation Criteria

Subjects may withdraw consent at any time for any reason or be withdrawn from the trial at the discretion of the investigator should any untoward effect occur. In addition, a subject may be withdrawn by the investigator or principal investigator if enrollment into the trial is inappropriate, the trial plan is violated, or for administrative and/or other safety reasons. Specific details regarding discontinuation or withdrawal are provided in Section 7.1.4 – Other Procedures.

A subject must be discontinued from the trial for any of the following reasons:

- The subject or legal representative (such as a parent or legal guardian) withdraws consent.
- Confirmed radiographic disease progression
- Unacceptable adverse experiences as described in Section 5.2.1.2
- Intercurrent illness that prevents further administration of treatment

- Investigator's decision to withdraw the subject
- The subject has a confirmed positive serum pregnancy test
- Noncompliance with trial treatment or procedure requirements
- The subject is lost to follow-up
- Administrative reasons

The End of Treatment and Follow-up visit procedures are listed in Section 6 (Protocol Flow Chart) and Section 7.1.5 (Visit Requirements). For those subjects discontinue treatment early, each subject will be followed for 30 days for adverse event monitoring (serious adverse events will be collected for 90 days after the end of treatment as described in Section 7.2.3.1). Subjects who discontinue for reasons other than progressive disease will have post-treatment follow-up for disease status until disease progression, initiating a non-study cancer treatment, withdrawing consent or becoming lost to follow-up. After documented disease progression each subject will be followed for overall survival until death, withdrawal of consent, or the end of the study, whichever occurs first.

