3. Radiation occurs continuously throughout therapy until the total of 35 fractions has been completed. Therefore, the dates listed may not always have radiation treatment on that date. All radiation should be completed by day 52.

4. For women of reproductive potential, a urine pregnancy test will be performed within 72 hours prior to the first dose of trial treatment. If urine pregnancy tests cannot be confirmed as negative, a serum pregnancy test, performed by the local lab, will be required. Pregnancy tests (serum and/or urine tests) should be repeated if required by local guidelines.

5. The serum chemistry panel includes tests listed in Section 7.1.3, Table 5(Albumin, AST, ALT, Alkaline phosphatase, Total Bilirubin (and direct bilirubin if elevated), Total Protein, CO2, Calcium, Chloride, Glucose, Potassium, Sodium, Creatinine, and BUN).

6. p16 immunohistochemistry status is required on all patients. This can be performed by the local laboratory sites. High risk HPV DNA testing at an outside lab can be performed if p16 staining is indeterminate or not able to be obtained. See section 5.1.2 for details.

7. Tumor tissue for biomarker analysis from an archival tissue sample or fresh biopsy must be provided for enrollment. Detailed instructions for tissue collection, processing and shipment are included in the procedures manual.

10. Blood for correlative flow cytometry studies will be drawn throughout treatment. On days with corresponding treatment, this should be drawn within 24 hours prior to treatment with pembrolizumab or chemotherapy. Procedures for sample collection, processing, and shipment are included in the procedures manual.

11. Patient reported outcomes (PRO) will be assessed using the FACT H&N form (see Appendix 11.8). PRO forms must be completed on paper or electronically by subjects prior to all other study procedures for that date. Patients who go off-treatment but continue follow up should be encouraged to complete PRO at the times outlined in the calendar.

12. Tumor imaging will be completed at baseline and after treatment has finished, on approximately day 150-157. Baseline imaging must be completed within 42 days of enrollment. Required imaging for the study protocol is diagnostic quality imaging of the neck. Additional imaging techniques can be utilized (i.e. MRI, FDG-PET, etc.), but are not required for study procedures.

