8.4.3.2 Table 7: Statistical Methods for Key Efficacy Endpoints

Patient Reported Outcomes (PRO)	Linear mixed model to compare with historical controls over time.	ASaT	Missing data will not be included	
1 – only those who undergo salvage surgery				

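### Nothing requires FACT-H&N after confirmed progression or new anti-cancer therapy, so the 1- and 2-year quality-of-life results will come mainly from patients without either and probably read too high for all living patients

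*Combined protocol and SAP*

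**What the plan says.** The QOL objective in Section 3.2 sets the time points as "during therapy, treatment end, and 1- and 2-years following treatment". Its hypothesis is that both acute and long-term QOL of participants "will be superior to historical controls". Neither is limited to patients whose disease stays controlled. The flow chart in Section 6.3 places the long-term FACT-H&N forms at follow-up visits 3 and 5.

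Section 7.1.5.6 sets the exit from that schedule: "Once a subject experiences confirmed disease progression or starts a new anti-cancer therapy, the subject moves into the Survival Follow-Up Phase". What follows is: "These subjects will be followed every 6 months to assess for survival status until death, withdrawal of consent, or the end of the study". Footnote 16 of the flow chart repeats this rule, and Section 5.9 agrees for progression: "After documented disease progression each subject will be followed for overall survival until death, withdrawal of consent, or the end of the study". The ordinary Follow-Up Phase is described in Section 7.1.5.5 for a different group: "Subjects who discontinue trial treatment for a reason other than disease progression will move into the Follow-Up Phase".

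Footnote 11 is the only rule on patient-reported outcomes that could reach these subjects: "Patients who go off-treatment but continue follow up should be encouraged to complete PRO at the times outlined in the calendar".

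For analysis, Table 7 gives a linear mixed model against historical controls in the ASaT population. Its missing-data entry reads: "Missing data will not be included". Section 8 plans no sensitivity analysis for forms missing because of outcome.

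**The concern.** The event that takes a patient off the questionnaire schedule is itself an outcome, and one that plausibly comes with worse QOL. If sites follow the plan as written, the 1- and 2-year averages will describe a selected group while being presented as the QOL of everyone treated.

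This bears on a decision. Section 4.2.3.2 treats QOL as important and says that a marked loss could argue against developing the regimen further, even if efficacy improves. The same section plans a comparison with about 50 patients given high-dose bolus cisplatin. If the two groups differ in how many patients progress, or in whether QOL was collected after progression, the comparison is between differently selected groups.

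**Working it through.** The plan states no power, SD, expected completion or progression rate for QOL, so there is no figure to reproduce. The check has four steps.

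**1. Which forms are affected.** Visit 3 falls 90 + 90 + 180 = 360 days after day 150. Visit 5 falls 360 + 180 + 180 = 720 days after day 150. A subject with confirmed progression or new therapy before those days is in Survival Follow-Up when the form falls due. Sections 5.9 and 7.1.5.6 and footnote 16 name survival there and no questionnaire. Footnote 17 asks patients who stop pembrolizumab to return so that QOL can be collected, but only up to day 150.

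**2. Size of the overstatement among living patients.** Let m be the mean of unaffected patients, f the share of living patients who have progressed or changed therapy, and D their mean deficit.

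- Mean of all living patients: (1 − f)m + f(m − D) = m − fD
- Mean of observed patients, if no affected patient completes a form: m
- Overstatement: f × D

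Both inputs are assumptions: f from 10% to 40%, D from 0.3 to 1.0 SD.

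| f | D = 0.3 SD | D = 0.5 SD | D = 1.0 SD |
|---|---|---|---|
| 10% | 0.03 | 0.05 | 0.10 |
| 20% | 0.06 | 0.10 | 0.20 |
| 30% | 0.09 | 0.15 | 0.30 |
| 40% | 0.12 | 0.20 | 0.40 |

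**3. Whether the mixed model repairs it.** Such a model can use a patient's earlier scores, but it sees no score after the event. I simulated 200,000 patients with scores at baseline, treatment end and one later time (coefficient 0.6 from each score to the next, unit SD, no deaths, about 30% affected). Each affected patient had a drop at the event. I compared the observed-only mean with a missing-at-random prediction from the earlier scores.

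| Drop at event | Event depends on earlier QOL? | Observed-only bias (SD) | Bias with earlier scores used (SD) |
|---|---|---|---|
| 0.5 SD | no | 0.15 | 0.15 |
| 0.5 SD | yes | 0.24 | 0.16 |
| 1.0 SD | no | 0.30 | 0.30 |
| 1.0 SD | yes | 0.39 | 0.31 |

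The earlier scores remove the part of the selection that they predict. The part caused by the drop at the event stays.

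**4. The comparison with historical controls.** With the same D in both groups, the bias is (f_trial − f_control) × D. Here f_control is the share of living controls whose forms are missing for the same reason, and is 0 if controls were followed regardless of progression. At D = 0.5 SD:

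- f_trial 40%, f_control 0: +0.20 SD
- equal shares: 0
- f_trial 10%, f_control 40%: −0.15 SD

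For scale, the standard error of a difference between 57 and 50 patients is √(1/57 + 1/50) = 0.19 SD, before any missing forms.

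**The case against.** The strongest reply is that no section says questionnaires stop at progression. Footnote 11 covers off-treatment patients who remain in follow-up and does not exclude progressed patients, and subjects in Survival Follow-Up are still followed. The flow chart also lists survival status and later anti-cancer therapy at visits 1 to 8, alongside FACT-H&N at visits 3 and 5. This stands as far as it goes: a reader might infer that collection is ordered to end, and the documents do not support that. What they show is that nothing requires it, and that sites could read the rules either way.

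It would also be too strong to say that the data will come only from progression-free patients. Progression must be confirmed before the move, and new therapy is a separate trigger. The documents do not say whether salvage surgery counts as new therapy.

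A further reply is that QOL is a secondary outcome in a single-arm phase IB trial, with treatment toxicity as its main rationale, so QOL while disease is controlled is a legitimate target. That is fair, but it is not the target that Section 3.2 and Table 7 state. The plan would need to say so.

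**Conclusion.** The gap in collection is real, and its likely effect is a long-term mean that is too high for living patients. The size is 0.03–0.40 SD on the assumed ranges, and 0.15 SD at f = 30% and D = 0.5 SD. This assumes that affected patients do not complete the forms and that their QOL is lower. The documents give neither f nor D, so overstatement is probable and not proven.

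Two stronger readings should be resisted:

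- **That the trial will look better than the controls.** How QOL was collected after progression in the controls is not stated, so the bias could be upward, downward or nil.
- **That the effect can be put in FACT-H&N points by applying a score gap to a share of all 57 patients.** The gap belongs to survivors, so the share must be of living patients. For illustration, suppose 15% of 57 (8.55) were affected, half of them had died and nobody else had. The share of living patients is then 4.3/52.7 = 8%, not 15%. The documents also give no score gap.

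The problem concerns a secondary outcome and is cheap to correct. It does not touch the primary endpoints.

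**What to change.** Amend Section 7.1.5.6 and footnotes 11 and 16 so that FACT-H&N is requested, by mail or electronically, at the visit 3 and visit 5 time points from living subjects in Survival Follow-Up. Bring Section 5.9 into line.

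Where those forms were not collected:

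- In Section 8.4.6, label the 1- and 2-year results as among patients alive and free of confirmed progression and new anti-cancer therapy, and state whether salvage surgery counts as new therapy for this purpose.
- Report the number alive and the number completing the form at each time point.
- Apply the same restriction to the historical controls. This needs their progression and therapy dates, so check first that these are available.
- Make no superiority claim for all participants.

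The cost is a short amendment and at most two extra questionnaires per affected living patient. The six-monthly survival contacts are not tied to visits 3 and 5, so a contact may have to be timed to those points. The labelling and reporting need no new data from trial patients.

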#### 7.2 Assessing and Recording Adverse Events

An adverse event is defined as any untoward medical occurrence in a patient that received a pharmaceutical product during the course of the study, whether or not they are considered related to the product. This includes changes in laboratory parameters. Any medical condition that is present before the subject starts study medication and does not deteriorate should not be reported as an AE. However, if it deteriorates at any time during the study it should be recorded as an AE.

Changes resulting from normal growth and development that do not vary significantly in frequency or severity from expected levels are not to be considered adverse events. Example of this may include, but are not limited to, menopause occurring at a physiologically appropriate time.

Adverse events may occur during the course of the use of Merck product in clinical trials or within the follow-up period specified by the protocol, or prescribed in clinical practice, from overdose (whether accidental or intentional), from abuse and from withdrawal.

Progression of the cancer under study is not considered an adverse event unless it is considered to be drug related by the investigator.

All acute adverse events will be recorded from the time the subject receives the first dose of treatment through 30 days following cessation of treatment. The reporting timeframe for adverse events meeting any serious criteria is described in section 7.2.3.1.

# 7.2.1 Definition of an Overdose for This Protocol and Reporting of Overdose to the Sanford Research and to Merck

For purposes of this trial, an overdose of pembrolizumab will be defined as any dose of 1,000 mg or greater ( $\geq$ 5 times the indicated dose). No specific information is available on the treatment of overdose of pembrolizumab. Appropriate supportive treatment should be provided if clinically indicated. In the event of overdose, the subject should be observed closely for signs of toxicity. Appropriate supportive treatment should be provided if clinically indicated.

If an adverse event(s) is associated with ("results from") the overdose of a Merck product, the adverse event(s) is reported as a serious adverse event, even if no other seriousness criteria are met.

If a dose of Merck's product meeting the protocol definition of overdose is taken without any associated clinical symptoms or abnormal laboratory results, the overdose is reported as a non-serious Event of Clinical Interest (ECI), using the terminology "accidental or intentional overdose without adverse effect."

Overdoses of radiation and cisplatin will be in accordance with the respective local product label and standard procedures.

All reports of overdose with and without an adverse event must be reported within 24 hours to Sanford Research and within 2 working days' hours to Merck Global Safety. (Attn: Worldwide Product Safety; [contact])

#### 7.2.2 Reporting of Pregnancy and Lactation to Sanford Research and to Merck

Although pregnancy and lactation are not considered adverse events, it is the responsibility of investigators or their designees to report any pregnancy or lactation in a subject (spontaneously reported to them), including the pregnancy of a male subject's female partner that occurs during the trial or within 120 days of completing the trial completing the trial, or 30 days following cessation of treatment if the subject initiates new anticancer therapy, whichever is earlier. All subjects and female partners of male subjects who become pregnant must be followed to the completion/termination of the pregnancy. Pregnancy outcomes of spontaneous abortion, missed abortion, benign hydatidiform mole, blighted ovum, fetal death, intrauterine death, miscarriage and stillbirth must be reported as serious events (Important Medical Events). If the pregnancy continues to term, the outcome (health of infant) must also be reported.

Such events must be reported within 24 hours to Sanford Research and within 2 working days to Merck Global Safety. (Attn: Worldwide Product Safety; [contact])

#### 7.2.3 Immediate Reporting of Adverse Events to Sanford Research and to Merck

#### 7.2.3.1 Serious Adverse Events

A serious adverse event is any adverse event occurring at any dose or during any use of Merck's product that:

- Results in death;
- Is life threatening;
- Results in persistent or significant disability/incapacity;
- Results in or prolongs an existing inpatient hospitalization;
- Is a congenital anomaly/birth defect;
- Is a new cancer (that is not a condition of the study);
- Is associated with an overdose;
- Is another important medical event

Refer to Table 6 for additional details regarding each of the above criteria.

Progression of the cancer under study is not considered an adverse event unless it results in hospitalization or death.

Any serious adverse event, or follow up to a serious adverse event, including death due to any cause other than progression of the cancer under study that occurs to any subject from the time the consent is signed through 90 days following cessation of treatment, or the initiation of new anti-cancer therapy, whichever is earlier, whether or not related to Merck product, must be reported within 24 hours to Sanford Research and within 2 working days to Merck Global Safety.

Non-serious Events of Clinical Interest will be forwarded to Merck Global Safety and will be handled in the same manner as SAEs.

Additionally, any serious adverse event, considered by an investigator who is a qualified physician to be related to Merck product that is brought to the attention of the investigator at any time outside of the time period specified in the previous paragraph also must be reported immediately to the principal investigator and to Merck.

